**Table 3. Treatment Arms for Part 2, Dose Expansion**

Treatment Arm	Number of Subjects
1: Subjects with advanced HCC who are FGF19-positive to receive H3B-6527 QD for 21-day cycles	40 subjects
2: Subjects with advanced HCC who are FGF19-positive to receive H3B-6527 BID for 21-day cycles	40 subjects

**Table 4. 2-sided 95% CI for ORR estimate up to 30% (40 subjects)**

ORR (N=40)	2-sided 95% CI
5% (2 responders in 40 subjects)	(0.006, 0.169)
7.5% (3 responders in 40 subjects)	(0.016, 0.204)
10% (4 responders in 40 subjects)	(0.028, 0.234)
12.5% (5 responders in 40 subjects)	(0.042, 0.268)
15% (6 responders in 40 subjects)	(0.057, 0.298)
17.5% (7 responders in 40 subjects)	(0.073, 0.328)
20% (8 responders in 40 subjects)	(0.091, 0.356)
22.5% (9 responders in 40 subjects)	(0.108, 0.385)
25% (10 responders in 40 subjects)	(0.127, 0.412)
27.5% (11 responders in 40 subjects)	(0.146, 0.439)
30% (12 responders in 40 subjects)	(0.166, 0.465)

Within each treatment arm, if both QD and BID dose schedules are studied, an evaluation using efficacy, safety, PK, pharmacodynamic data will be performed and the investigators and Sponsor will jointly determine if one dose schedule is better than the other.

## 5 STATISTICAL METHODS

All statistical analyses and summary information are to be generated according to this SAP. Any deviations from this SAP will be documented in the clinical study report (CSR).

Unless otherwise stated, tables, listings, and graphs (TLGs) for Dose Escalation (Part 1) will be broken down by dose cohort, for Expansion (Part 2) by QD/BID dose schedule.

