Once a subject has completed C3 at the initially assigned dose schedule and dose level (QD or BID), intrapatient dose escalation will be allowed. Only subjects who have not progressed on treatment and did not have a dose reduction or interruption because of a drug-related AE, will be permitted to escalate to the highest dose level that has completed DLT assessment within that dose schedule and has been shown to be safe (no DLT in the first 3 subjects or no more than 1 DLT in 6 subjects). Subjects on the intrapatient dose escalation will not be included in the DLT analysis at the higher dose level. The investigator and the medical monitor must agree that dose escalation is appropriate for the subject prior to escalating their H3B-6527 dose level.

The starting dose of 300 mg QD (first-in-human dose) is the HED of 1/6th the HNSTD in dog. Dose escalation will follow a modified Fibonacci design such that the magnitude of the escalation will decrease as the dose level nears the HED of the HNSTD in dogs (HED \approx 2000 mg).

Table 1 Dose Cohorts in H3B-6527 Dose-Escalation

Dose Level	Initial No. of Subjects	H3B-6527 Total Daily Dose
-1	3	150 mg
1 ^a	3	300 mg
2	3	600 mg
3	3	1000 mg
4	3	1400 mg
5	3	2000 mg

These total daily dose levels may be evaluated in QD or BID dose schedules, including intermediate dose levels, and in expansion of an existing dose level of up to 12 evaluable subjects following discussions between the Sponsor and the investigators, if supported by evolving safety, tolerability, PK, and pharmacodynamic data.

BID = twice daily, PK = pharmacokinetic, QD = once daily.

a: Planned starting dose level in QD schedule.

Refer to [Section 9.4.4.1](#) for details regarding the dose-escalation procedure.

The MTD is defined as the highest dose at which no more than 1 of 6 subjects experiences a DLT in the dose cohort. (Note that at least 6 subjects must be treated at the dose level potentially considered to be the MTD before that dose level can be considered the MTD). Therefore, if ≥ 2 subjects within a cohort experience a DLT and the previous dose level did not enroll 6 subjects, enrollment will move down to the previous dose level and continue until 6 subjects are enrolled, and the same guidelines for determining the MTD will be followed.

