9.4.4 Method of Assigning Subjects to Treatment Groups

The dose level to which a subject is assigned is dependent on the study part and cohort into which the subject is enrolled.

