### 3.2.2 Dose Escalation (Part 1)

The objective of the Dose Escalation phase is to determine the MTD and/or RP2D of H3B-6527 in subjects with advanced HCC. Intrahepatic cholangiocarcinoma (ICC) subjects were also enrolled from protocol Amendment 5 to Amendment 7.

For dose-escalation purposes, toxicities assigned as DLTs during the first cycle will be assessed. After 3-6 subjects in a cohort have completed Cycle 1 (C1), all available safety data will be reviewed by the Safety Review Committee (SRC) consisting of Sponsor personnel and investigators and the decision to proceed to the next dose cohort will be made jointly. Toxicities will be graded using the National Cancer Institute (NCI) Common Terminology Criteria for Adverse Events (CTCAE) version 4.03.

Once a subject has completed C3 at the initially assigned dose schedule and dose level (QD or BID), intrapatient dose escalation will be allowed.

H3B-6527 will be tested in sequential escalating dose cohorts (n=3 to 6) at the dose levels listed in the Table 1.

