### Definitions of DLT and MTD

The DLTs are defined as any of the toxicities listed in Table 2 occurring during C1 and judged by the investigator as related to study drug (i.e., assessed as unrelated to disease, intercurrent illness, or concomitant medications).

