## 5.6 Safety Analyses

All safety analyses will be performed on the Safety Analysis Set and “as treated” basis except the evaluation of DLT and determination of the MTD. The number (percentage) of DLT will be summarized on and the determination of the MTD will be based on DLT Analysis Set in the Dose Escalation part.

Subjects who do not receive study drug for at least 17 of 21 days (80%; not necessarily consecutively) during the first cycle for reasons not considered to be a DLT by both the investigators and the Sponsor will be replaced. The subjects who are replaced will not be considered evaluable for DLT assessments.

Safety data include all AEs, SAEs, clinical laboratory tests, vital signs, ECGs, MUGA/echocardiogram, and ophthalmic examinations.

Safety parameters will be summarized using descriptive statistics (mean, standard deviation, median, Q1, Q3, and range for continuous variables; numbers and percentages for categorical measures).

The effects of H3B-6527 on cardiovascular repolarization will be evaluated via 12-lead continuous cardiac Holter monitoring around first dose administration on C1 Day 1 and Day 8 in the dose escalation part of the study only. Individual ECGs will be extracted from the Holter recordings at specified time points per ECG manual and will be evaluated by a central laboratory. QT intervals will be measured from Lead II and will be corrected for heart rate (QTc) using Fredericia’s (QTcF) correction factors. The primary QTc parameter will be QTcF; secondary parameters (QTc corrected using Bazett’s formula [QTcB], QT, QRS, PR, and heart rate) and wave forms (T waves) will be evaluated.

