### 5.6.1 Extent of Exposure

The extent of exposure of study drug will be summarized for the Safety Analysis Set by number of cycles/days on treatment, duration of treatment, total dose, the number of cycles received and the number of subjects requiring dose reductions, treatment delay and treatment discontinuation due to AEs. A subject listing of study drug administration by cycle/visit will be provided.

The treatment compliance will be summarized for the Safety Analysis Set by dose intensity and received dose as percentage of planned starting dose.

Duration of treatment (days) = last dose date of study drug – first dose date of study drug +1.

Dose intensity (mg/day) = total dose received during the study / (duration of treatment in days)

Received dose as percentage of planned starting dose (%) =  $100 \times$  dose intensity (mg/day) / planned starting dose (mg/day).

Listings of study drug administration by cycle/visit and treatment exposure will be provided.

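### The SAP does not say which dose carries data collected after intrapatient escalation, and its compliance ratio can exceed 100% for escalated subjects who miss doses

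*SAP*

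**What the plan says.** - **Grouping.** SAP section 5 sets the default for Part 1 outputs: "tables, listings, and graphs (TLGs) for Dose Escalation (Part 1) will be broken down by dose cohort". Protocol 9.4.4 indicates what a cohort means for dose: "The dose level to which a subject is assigned is dependent on the study part and cohort into which the subject is enrolled". Protocol 9.7.1.8.2 groups TEAEs by study part and cohort. SAP 5.6.2 counts a subject once per system organ class and preferred term, and does not mention the dose being taken at onset.
- **Escalation.** SAP 3.2.2: "Once a subject has completed C3 at the initially assigned dose schedule and dose level (QD or BID), intrapatient dose escalation will be allowed". Protocol 9.1.1.1 adds that subjects without progression, and without a reduction or interruption for a drug-related event, "will be permitted to escalate to the highest dose level that has completed DLT assessment within that dose schedule".
- **Analysis rule for escalated subjects.** There is one, in Protocol 9.1.1.1: "Subjects on the intrapatient dose escalation will not be included in the DLT analysis at the higher dose level". DLTs are events "occurring during C1 and judged by the investigator as related to study drug", so they precede any escalation.
- **Safety basis.** SAP 5.6 says analyses are "performed on the Safety Analysis Set and “as treated” basis except the evaluation of DLT and determination of the MTD". It does not say how this works for a subject who has taken two doses.
- **Exposure.** SAP 5.6.1 summarises treatment compliance by dose intensity and by "received dose as percentage of planned starting dose".
- **Extension Phase.** Protocol 9.1.2.3 and SAP 3.2.4 say subjects stay on the dose they had in the Treatment Phase, which lasts one cycle. Neither passage mentions the escalation allowed after Cycle 3.

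**The concern.** Dose labels in a Part 1 table are read as the dose that produced the result. Once a subject escalates, the enrolled cohort and the dose being taken differ, and the plan has no rule for the data that follow. Safety and tolerability are a primary objective. Toxicities after Cycle 1 that would otherwise meet the DLT definition may be considered when the RP2D is chosen. An event arising at a higher dose but shown in a lower-dose column inflates the lower column and blurs the dose-toxicity gradient. Two programmers following the same SAP could also produce different adverse event tables.

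The compliance ratio is a separate problem, because there the formula is explicit. The denominator stays at the starting dose while the numerator rises with escalation, so the result no longer measures compliance.

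**Working it through.** **1. Cohort sizes.** The plan's Part 1 range reproduces: 5 QD levels × 6 = 30, and (5 + 3) levels × 6 = 48. SAP 3.2.2 gives cohorts of 3 to 6, with expansion of a level to 12 possible.

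**2. When data can fall after escalation.** A cycle is 21 days (Protocol 9.4.1), so Cycle 3 ends on Day 3 × 21 = 63 and the earliest escalation is Day 64. Protocol 9.1.2.4 anticipates about 4 months on treatment, taken here as 120 to 122 days.
- Time after Cycle 3: 120 − 63 = 57 days (47.5%), to 122 − 63 = 59 days (48.4%).
- Scans: Week 6 (6 × 7 = Day 42) precedes escalation. Week 12 (12 × 7 = Day 84) and later scans can follow it.

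**3. Efficacy.** In SAP 5.1.2, time to response and PFS run from first dose, and ORR covers the period from first dose to progression. SAP Table 5 has no entry for escalation, and nothing overrides the cohort breakdown. A response first documented at Week 12 or later, after escalation, is therefore credited to the starting dose.

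**4. Adverse events.** Take a hypothetical 6 subjects at 300 mg and 6 at 1000 mg. One 300 mg subject escalates to 1000 mg and then has the only Grade 3 event.

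| Reading | 300 mg column | 1000 mg column |
|---|---|---|
| By enrolled cohort | 1/6 = 16.7% | 0/6 = 0% |
| By dose at onset, escalator added to the higher denominator | 0/6 = 0% | 1/7 = 14.3% |

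Both readings are compatible with the SAP; Protocol 9.7.1.8.2 points to the first. The shift from one subject is 1/3 = 33.3, 1/6 = 16.7 or 1/12 = 8.3 points. Precision is poor in any case: the exact 95% interval is 0% to 45.9% for 0/6 and 0.4% to 64.1% for 1/6.

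**5. Compliance ratio.** SAP 5.6.1 defines dose intensity as total dose ÷ duration of treatment, and the ratio as 100 × dose intensity ÷ planned starting dose. Take 63 days at 300 mg and then 59 days at 600 mg.
- All doses taken: (63 × 300 + 59 × 600) / 122 = 54,300 / 122 = 445 mg/day; 445 / 300 = 148%.
- A quarter of the later doses missed: (18,900 + 0.75 × 35,400) / 122 = 45,450 / 122 = 372.5 mg/day; 372.5 / 300 = **124%**.
- The same subject against the dose planned at each time: 45,450 / 54,300 = 83.7%.

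Three cycles at 300 mg followed by three at 1000 mg, with full adherence, give (300 + 1000) / 2 / 300 = 217%.

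**6. Outputs not affected.** DLT and MTD results use Cycle 1 (SAP 5.2.1). PK sampling is in Cycle 1 (Protocol Table 6). Holter recordings are on Cycle 1 Days 1 and 8 (SAP 5.6).

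**The case against.** The strongest reply is that adverse event attribution is open, not wrong. The SAP default yields to any other statement, SAP 5.6 invokes an as-treated basis, and SAP 8, 9 and 11 place derivation rules and table shells in documents not available here. That stands: for adverse events the finding is an undefined rule with a likely default.

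Other parts of the reply also stand:
- A reader might infer that high doses will look safer. The documents do not support this in absolute terms. Under enrolled-cohort grouping an escalated subject is in neither the numerator nor the denominator of the higher column, so that column does not change. Only the lower column can be inflated, which narrows the contrast.
- A reader might infer that every Part 1 table except the DLT table is affected. The Cycle 1 outputs are not, and laboratory grades are also tabulated by cycle (SAP 5.6.3).
- A reader might infer that missed doses cannot be seen. SAP 5.6.1 also reports total dose, duration, reductions and delays, with administration listings, and the ratio is openly labelled as relative to starting dose. It is the compliance summary that misleads; the data are not lost.
- The RP2D is agreed by the Safety Review Committee from an integrated review before Expansion. Nothing says it relies on the final cohort tables.
- The antitumor objective concerns FGF19-positive subjects at the RP2D, which is the Part 2 population. Part 1 efficacy is descriptive, and grouping it by assigned dose is defensible if labelled.
- Escalators are selected for tolerance and lack of progression. Truncating cohort tables at escalation would discard the follow-up of the best tolerators and assign cumulative toxicity wholly to the current dose. This argues for a supplementary table, not a replacement.

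The reply does not supply a rule for post-escalation data, and it does not rescue the compliance ratio.

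**Conclusion.** The point holds as a gap in the SAP plus one formula that misleads. Responses first documented after escalation fall under the starting dose by the plain reading of SAP 5. TEAEs do so by default, with the as-treated basis left undefined. The compliance ratio can read 124% for a subject who took 83.7% of the dose planned over time.

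The number of escalators is not given, so the effect on any table is conditional. Each misplaced subject is worth 33 points in a cohort of 3 and 17 in a cohort of 6. The exposure examples assume escalation on Day 64; the 122-day ones also assume the anticipated 4 months of treatment. A move from 300 to 2000 mg is a tempting extreme. However, five sequential levels need at least 5 × 21 = 105 days to clear their DLT cycles, so a subject in the first 300 mg cohort could reach 2000 mg only late in that period.

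The documents do not support a conclusion that the MTD is biased or that higher doses would be shown as safer than they are. This should be corrected before database lock, but it does not threaten the dose-escalation decision rule.

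**What to change.** In the SAP:
1. **Section 5:** state that dose cohort means the initially assigned dose and schedule, and keep the by-cohort tables on that basis.
2. **Section 5.6:** define the as-treated basis for a subject who takes more than one dose level. Add a supplementary TEAE table by dose at onset for subjects who escalate, giving the number of escalators and their time at each dose.
3. **Section 5.4.1:** flag, in the response table and listing, any response first documented after the first escalated dose.
4. **Section 5.6.1:** compute relative dose intensity as total dose received divided by the total dose planned over the same days, with the planned dose updated at each permitted escalation. State whether a dose reduction lowers the planned dose; if it does, reductions drop out of the ratio and need their own line.

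The Extension Phase statements in Protocol 9.1.2.3 and SAP 3.2.4 must also be reconciled with the escalation provision in Protocol 9.1.1.1 and SAP 3.2.2. Which should prevail is for the sponsor to decide.

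The cost is SAP wording, a few extra tables and some programming. Dosing dates and doses are already to be listed by subject (Protocol 9.7.1.8.1, SAP 5.6.1), so no new data are needed. The supplementary table will be small and drawn from a selected group, and should be labelled descriptive.

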### 5.1 Study Endpoints

#### 5.1.1 Primary Endpoints

- Occurrence of DLTs as a function of the dose of H3B-6527 for determination of the MTD and RP2D.
- Safety/tolerability: the type and frequency of AEs, serious adverse events (SAEs) using CTCAE, Version 4.03, as well as changes in clinical laboratory values, electrocardiogram (ECG) parameters and vital sign measurements.

#### 5.1.2 Secondary Endpoints

- PK: standard primary PK parameters including, but not limited to, the area under the plasma concentration-time curve from 0 through last measurable point (AUC0-t), maximum observed plasma concentration (Cmax) and time of maximum observed plasma concentration (tmax).
- Preliminary antitumor activity: Response will be determined by the investigator using mRECIST/RECIST 1.1. The following endpoints will be determined:
  - Objective response rate (ORR), defined as the proportion of subjects achieving a best overall confirmed response of partial or complete response (partial response [PR] + complete response [CR]) from first dose date until disease progression/recurrence.
  - Duration of response (DOR), defined as the time from the date of first documented CR/PR until the first documentation of disease progression as determined by the investigator or death, whichever comes first. If a subject had no record of disease progression or did not die before the data cut-off date, then the subject will be censored at the last available tumor assessment.
  - Progression free survival (PFS), defined as the time from first dose date to the date of the first documentation of disease progression as determined by the investigator or death, whichever occurs first.

- Overall survival (OS), defined as the time from first dose date to the date of death.
- Time to response, defined as the time from first dose date to the date of first documented CR/PR.

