9.1.2.4 Follow-Up Phase

After the Off-treatment Visit (OTV), all subjects who discontinue study treatment, regardless of their reasons for doing so, will be followed for survival via telephone (for those subjects who experience PD or initiate a new anticancer therapy) or office visit (for those subjects still undergoing tumor assessments). Subjects will be followed for survival approximately every 12 weeks for up to 12 months or until 6 cycles after last patient in, death, loss to follow-up, or withdrawal of consent, whichever occurs first. Subjects who discontinue study drug and

have not experienced PD will continue to undergo tumor assessments every 6 weeks until documented PD or another anticancer therapy is initiated.

The data cutoff for the primary analysis will occur once the last subject completes 6 cycles of investigational therapy. Subjects will be allowed to continue treatment until progression or the end of therapeutic benefit from the study drug as determined by Sponsor discussion with investigator.

The end of the study is defined as when the last ongoing subject completes their off treatment visit. The off treatment visit should occur 30 days after final dose with a window of ± 3 days.

The maximum estimated period for each subject on treatment is anticipated to be approximately 4 months. However, subjects may continue to receive study treatment, as long as they demonstrate clinical benefit as judged by the investigator after discussion with the Sponsor or until the end of the study.

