During the Follow-up Period, subjects who discontinue study treatment without objective evidence of PD will continue to have tumor assessments (including brain scans as clinically indicated) performed every 6 weeks from the date of last tumor assessment, or sooner if clinically indicated, until PD is documented.

The tumor assessment schedule should not be affected by interruptions in therapy or any other events.

Tumor assessments will be performed following mRECIST guidance ([Appendix 1](#)) for HCC using triphasic liver CT/MRI (optimized for precontrast, arterial phase, and portal venous phase).

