9.5.5 Completion/Discontinuation of Subjects

The investigator may discontinue study drug for a subject at any time for safety or administrative reasons. A subject may elect to discontinue study drug and study participation at any time for any reason. All subjects who discontinue study drug are to complete the Off-Treatment visit, as indicated in the Schedule of Procedures/Assessments [Table 6](#) and [Table 7](#).

Study drug is to be discontinued for the following reasons:

- Progression of disease that, in the opinion of the investigator, precludes further study treatment. (After consultation with the Sponsor, H3B-6527 may be continued for a subject who has met the criteria for PD but, in the investigator's opinion, is receiving benefit.)
- Occurrence of an unacceptable AE.
- Subjects who do not receive study drug for at least 17 of 21 days (approximately 80%, not necessarily consecutively) during the first cycle for reasons not considered to be a DLT by both the investigators and the Sponsor will be replaced. The subjects who are replaced will not be considered evaluable for DLT assessments.
- Subject requires use of a prohibited concomitant medication or therapy.
- General or specific changes in the subject's condition unacceptable for further treatment within the study parameters, in the judgment of the investigator.
- Non-compliance.
- Lost to follow-up.
- Subject, investigator, or Sponsor request.

The reason for study drug discontinuation is to be documented in the CRF.

Subjects who discontinue study drug for reasons other than PD are to continue to have tumor measurements and disease response assessments performed every 6 weeks until the development of PD. After development of PD, subjects who discontinue study treatment, regardless of their reasons for doing so, will be followed for survival approximately every 12 weeks for up to 12 months or until 6 cycles after last patient in, death, loss to follow-up, or withdrawal of consent, whichever occurs first. However, subjects may continue to receive study treatment, as long as they demonstrate clinical benefit as judged by the investigator after discussion with the Sponsor or until the end of the study.

Study participation also may be discontinued for any of the following reasons:

- Subject withdrawal of consent
- Non-compliance
- Lost to follow-up
- Sponsor request
- Closure of the study by the Sponsor.

The reason for study discontinuation is to be documented in the CRF.

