### 5.4.1 Analysis of Efficacy Endpoints Based on Tumor Response

ORR, duration of response (DOR), time to response and PFS will be analyzed on the FAS for HCC subjects and Response Evaluable Set as appropriate.

The exact 95% confidence intervals of ORR will be calculated using Clopper-Pearson method. DOR and time to response will be for subjects who have achieved a best response of CR or PR only. Censoring rules for PFS will follow the FDA guidance and are specified in Table 5. PFS will be reported in both summary tables and plotted with Kaplan-Meier curve.

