**Table 5 Censoring Rules for PFS**

No.	Situation	Date of Event (Progression/Death) or Censoring	Outcome
1	No baseline tumor assessments	Date of first dose	Censored
2	Progression documented between scheduled visits	Date of first radiologic PD assessment	Event
3	No progression	Date of last adequate radiologic assessment	Censored
4	New anticancer treatment started	Date of last adequate radiologic assessment prior to or on date of new anticancer treatment	Censored
5	Death before first PD assessment	Date of death	Event
6	Death between adequate assessment visits*	Date of death	Event
7	Death or progression after more than one missed visit/tumor assessment**	Date of last adequate radiologic assessment before missed tumor assessments	Censored

CR = complete response, PD = progressive disease, PR = partial response, SD =stable disease,

\* Adequate tumor assessment is radiologic assessment of CR, PR, SD, non-CR/non-PD or PD at regular interval as defined in the protocol.

\*\* More than one missed visit/adequate tumor assessment is defined as having either one of the following two durations being longer than 14 weeks - 1 day, which is 97 days ( $= ((6+1) \times 2 \times 7) - 1$ ) for subjects on the every 6 week tumor assessment schedule:

- Duration between two consecutive tumor assessments
- Duration between the last adequate tumor assessment and death or PD

The priority of the censoring rules is as follows,

- If the subject had PD or death, the following sequence will be applied:
  - If a subject did not have a baseline tumor assessment (No. 1), the subject will be censored on the date of first dose.
  - If the subject died within 97 days (14 weeks -1 day) following first dose and did not receive a new anticancer treatment, it will be counted as PFS event at the date of death.

- If a subject had new anticancer treatment before PD or death (No. 4), the subject will be censored on the date of the last adequate tumor assessment prior to or on the date of new anticancer treatment.
- If a subject missed two or more tumor assessments before PD or death (No. 7), the subject will be censored on the date of the last adequate tumor assessment before PD or death. Note that if a subject is censored by both this criterion and the anticancer treatment criterion, the earliest censoring date will be used.
- Otherwise, if a subject had an event (No. 2, No. 5, or No. 6), the earliest event date will be used.

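### DOR lacks the new-therapy and missed-assessment censoring that PFS has, so a responder's DOR can end in an event after PFS is censored, and can exceed that PFS

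*SAP*

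**What the plan says.** **DOR.** SAP 5.1.2 defines it as "the time from the date of first documented CR/PR until the first documentation of disease progression as determined by the investigator or death". If neither has occurred by cut-off, "then the subject will be censored at the last available tumor assessment". No other DOR censoring rule is given. Protocol 9.7.1.1 and 9.7.1.6 and SAP 5.3.5 add none.

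**PFS.** SAP 5.4.1 states: "Censoring rules for PFS will follow the FDA guidance and are specified in Table 5". For a subject who starts new anticancer treatment, row 4 of that table sets the censoring date as "Date of last adequate radiologic assessment prior to or on date of new anticancer treatment". Row 7 censors at the last adequate scan when progression or death follows more than one missed assessment, defined as a gap longer than 97 days.

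**ORR and time to response.** The ORR window in SAP 5.1.2 is "from first dose date until disease progression/recurrence". Time to response runs from first dose to first CR/PR. Neither mentions new therapy.

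**Data after new therapy.** Protocol 9.1.2.4 keeps subjects "followed for survival via telephone (for those subjects who experience PD or initiate a new anticancer therapy", so later deaths are recorded. The statements on scans differ:
- They stop at PD or new therapy in the Protocol Synopsis (Follow-up Phase and Efficacy Assessments), Protocol 9.1.2.4, footnote x of Table 6, footnote u of Table 7, and SAP 3.2.4.
- The follow-up paragraph of Protocol 9.5.1.2.1 has scans continue "every 6 weeks from the date of last tumor assessment, or sooner if clinically indicated, until PD is documented".
- Protocol 9.5.5 asks for "disease response assessments performed every 6 weeks until the development of PD".

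**The concern.** Response starts after first dose, so DOR measured to the same end date cannot be longer than PFS in the same subject. Here the two endpoints have different end rules. PFS closes at the last scan before a treatment switch, or before a run of missed scans. DOR stays open to a later death, whatever was given in between.

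Two consequences follow. A reader can meet a responder whose DOR outlasts the reported PFS, with no stated reason. And the part of DOR after a switch reflects the next treatment as well as H3B-6527. DOR is read alongside ORR, the one endpoint with tabulated Part 2 precision. Efficacy data also feed the QD-versus-BID judgement in Protocol 9.7.2 and SAP section 4.

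**Working it through.** **The plan's own figure.** The missed-assessment window is ((6 + 1) × 2 × 7) − 1 = 97 days, as Table 5 states.

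**Assumed timeline.** The documents give no subject dates, so these are illustrative: first dose Day 1, PR Day 43, confirming and last scan Day 85. Duration = end − start + 1.

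**1. Row 4 on its own.** New therapy Day 100, death Day 160.
- Gap from last scan to death: 160 − 85 = 75 days, inside 97, so row 7 is not triggered.
- Death falls 159 days after first dose, and new therapy was given, so the early-death clause in the priority list does not apply.
- PFS: row 4 censors at Day 85, giving 85 − 1 + 1 = **85 days, censored**.
- DOR: 160 − 43 + 1 = **118 days, event**.

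**2. Same dates without new therapy.** PFS is an event at 160 days and DOR an event at 118 days, which is consistent. The conflict in step 1 comes from row 4 alone.

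**3. Range of death dates.** DOR exceeds PFS when D − 43 + 1 > 85, that is, from Day 128. Row 7 stays silent while D − 85 ≤ 97, that is, up to Day 182. Between those days row 4 alone makes DOR longer than PFS. For deaths from Day 100 to Day 127, DOR is still an event while PFS is censored, but it is not longer.

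**4. Row 7 on its own.** No new therapy, no further scans, death Day 260. The gap is 260 − 85 = 175 days, above 97. PFS is censored at 85 days; DOR is an event at 260 − 43 + 1 = **218 days**. Adding only row 4 to DOR would leave this case inconsistent.

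**5. Both rows applied to DOR.** In steps 1 and 4 DOR becomes 85 − 43 + 1 = **43 days, censored**. PFS and DOR then share an end date, so DOR cannot exceed PFS.

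**6. Direction of the median.** Assume four DOR events at 10, 12, 20 and 30 weeks, and take the median as the first time S ≤ 0.5. As written, S is 0.75 at week 10 and 0.50 at week 12, so the median is 12.
- If the 10-week event is a death after new therapy with the last scan at week 6 of response, it is censored at 6. Three remain at risk: S = 2/3 at week 12 and 1/3 at week 20. The median rises to **20**.
- If instead the 20- and 30-week events are such deaths, each censored at 6, two remain: S = 1/2 at week 10. The median falls to **10**.

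**7. ORR and time to response, only if scans continue after new therapy.** Stable disease to Day 85, new therapy Day 100, PR Day 127 confirmed Day 169: the subject counts as a responder with a time to response of 127 days, while PFS is censored at 85 days. One such responder is 1/40 = 2.5 percentage points of an arm; for example, 2/40 (0.006, 0.169) becomes 3/40 (0.016, 0.204).

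**The case against.** **Counting every death is a legitimate choice.** It can be, as a treatment-policy definition. But the SAP does not declare it for DOR, and it does the opposite for PFS.

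**The rule may sit in the programming specifications.** SAP sections 8 and 9 defer further conventions to documents that are not available here, so this cannot be excluded. SAP section 5 says analyses follow the SAP, and the SAP spells the rule out for PFS. The DOR rule belongs beside it.

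**The DOR censoring sentence joins its two conditions with 'or'.** Read literally, it would censor a responder who died without PD, which removes the conflict. It would also censor a subject with PD who is alive, leaving as events only those with both outcomes. That contradicts the definition just before it, so I read it as neither PD nor death.

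**Two stronger readings a reader might infer.**
- *The missing new-therapy rule inflates DOR several-fold.* Take PR at week 6, last scan week 18, new therapy week 20 and death week 60. DOR is 54 weeks against 12 weeks of observed response, or 4.5 times. But the gap from last scan to death is 42 × 7 = 294 days, so row 7 censors PFS even without new therapy. Where scans stop at new therapy, row 4 alone explains at most 12 + 97/7 ≈ 25.9 weeks, about 2.2 times.
- *Responses on later treatment are routinely credited to H3B-6527 in ORR.* Most statements, including the SAP's own, stop scans at new therapy. Only the follow-up paragraph of Protocol 9.5.1.2.1 and Protocol 9.5.5 lack that stop. The former closely parallels the Table 6 and 7 footnotes that have it, so the omission may be accidental. Footnote b of those tables follows subjects to PD or death but does not mention scans. This part is possible, not established.

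It also stands that these are secondary, descriptively summarised endpoints, and that responses at every time point will be listed.

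**Conclusion.** The DOR point holds however the scan statements are reconciled, because deaths after new therapy are collected and the definition counts them. Under the SAP's own rules one subject can have PFS censored at 85 days and a DOR event at 118 days, with row 4 the only cause. Missed assessments open a second route through row 7. Both results use assumed dates and the reading of the censoring sentence given above.

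The number of subjects affected cannot be computed. It requires a responder who leaves treatment without PD, then starts new therapy or misses scans, then has an event before cut-off; the documents give no rate for any of these. A reader might infer that DOR is flattered, but the direction is not fixed: censoring these deaths can raise or lower the Kaplan-Meier median. No alpha or power is involved. For ORR and time to response, the gap matters only if scans are taken after new therapy. The change should be made before database lock.

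**What to change.** In SAP 5.1.2 and 5.4.1:

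1. Replace the DOR censoring sentence with a statement that DOR uses the Table 5 censoring rules, naming both row 4 (new anticancer treatment) and row 7 (missed assessments).
2. As a safeguard, state that best overall response, including the confirming scan, and time to response use only assessments on or before the start of new anticancer therapy.

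In the protocol, reconcile the follow-up paragraph of 9.5.1.2.1 and section 9.5.5 with the Synopsis, 9.1.2.4, footnote x of Table 6, footnote u of Table 7, and SAP 3.2.4 on when protocol scans stop. The two analysis rules work whichever way that is settled.

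The cost is a few lines of text and code. Footnote b of Tables 6 and 7 already has anticancer therapies collected, and PFS already needs the start date of new therapy and the dates of adequate scans. Reported DOR may change in either direction; ORR could only stay the same or fall.
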